2. Age \geq 18 years of age
3. No receipt of convalescent plasma

Immunologic Controls:

1. PBMCs with 5-10 million cryopreserved cells per specimen present in the prospective COVID 19 Biorepository
2. Serum or plasma 500 UI each from up to 50 patients present in the COVID-19 Biorepository

Assessment and Data Acquisition:

1. Baseline: Age, sex, comorbidities, date of symptom onset, known COVID-19 contact, type of admission to the floor or ICU, APACHE score (ICU scoring system to classify disease severity and mortality risk), SOFA score (mortality prediction score based on organ function), clinical status, vital signs including temperature, respiratory rate, oxygen saturation, oxygen requirement, neutrophil count, lymphocyte count, CRP, chest x-ray, chest CT, location in hospital.
2. Safety and efficacy: Day 0 (baseline), 1, 2, 3, 4, 7, 14, 21, and 28 and once at day 60.
3. SARS-CoV-2 PCR from OP or NP swabs: Day 0, 4, 7, 14 and at any time when there is clinical suspicion for COVID-19.
4. Outcome measures: increased O₂ requirement (PaO₂/FiO₂ ratio or SpO₂/FIo₂), supplemental oxygen strategy (nasal cannula, high flow nasal cannula, noninvasive ventilation, intubation and invasive mechanical ventilation, rescue ventilation i.e. neuromuscular blocking agents, prone positioning, corticosteroids, ECMO), vasopressors, renal support, ICU LOS, ICU mortality, hospital LOS, hospital mortality, 28 day mortality.
5. Serum or plasma antibody titer² to SARS-CoV-2: Day 0, 7, 14, and 28. Samples from the COVID-19 Biorepository from non-transfused patients will be assayed at two similar timepoints as Immunologic Controls.
6. Blood for immune evaluations of cellular and humoral immunity before CIP infusion (day 0) and 7, 14 and 28 days after CIP infusion. Immune testing may be done at any time if the PI determines there is a need to evaluate acute immune responses (cytokines/chemokines levels). Samples from the Prospective COVID-19 Biorepository from non-transfused patients will be assayed at two similar timepoints as Immunologic Controls.
7. "Clinical controls" will have all relevant datapoints collected via chart review (i.e. biospecimens will not be collected prospectively)

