2.3 Study Design

This is a single arm phase II trial to assess preliminary efficacy and confirm safety of infusions of anti-SARS-CoV-2 convalescent plasma in hospitalized patients with acute respiratory symptoms **with or without** confirmed interstitial COVID-19 pneumonia by CXR or chest CT. A total of 29 eligible subjects will be enrolled to receive high titer anti-SARS-CoV-2 plasma. Participants will be compared to a historical control group via retrospective chart review.

In addition, the following Immunologic Controls will be used to meet secondary objectives described above:

1. PBMCs with 5-10 million cryopreserved cells per specimen will be obtained from the prospective COVID 19 Biorepository (2 timepoints per patient t (60 specimens total) and assessed for cellular and humoral immune responses.
2. Serum or plasma 500 UI each from up to 50 patients in the Covid-19 Biorepository will be collected (2 timepoints from each patient) (100 total specimens) will be evaluated for antibody and cytokine responses.

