3.2 Experience with the use of convalescent immune plasma against coronavirus diseases

In the 21st century, there were two coronavirus epidemics associated with high mortality. The SARS outbreak in 2003 and MERS outbreak in 2012 had high mortalities and absence of effective therapies which led to the use of convalescent immune plasma. The largest study with SARS using convalescent immune plasma involved the treatment of 80 patients in Hong Kong⁷. **Patients treated before day 14 after onset of symptoms had an improved prognosis as measured by discharge from hospital before day 22.** Furthermore, those who were RT-PCR positive and seronegative for coronavirus at the time of therapy had improved prognosis. Three seriously ill patients recovered from SARS in Taiwan were treated with 500 ml of convalescent plasma which led to a reduction in plasma virus titer⁸. Three patients with MERS in South Korea were treated with convalescent plasma, but only two of the recipients had neutralizing antibody in their plasma⁹. The results suggests that providing passive antibodies may suppress the development of high titers of neutralizing antibodies to the pathogen¹⁰. The analysis of 99 samples of convalescent sera from patients with MERS showed that 87 had neutralizing antibody with a geometric mean titer of 1:61. These data suggest that antibody declines with time and/or that few patients make high titer responses. There are reports that convalescent plasma was used for therapy of patients with COVID-19 in China during the current outbreak. Although few details are available from the Chinese experience and published studies involved small numbers of patients, the available information suggests that convalescent plasma administration reduces viral load and was safe. Because of these early suggestions of benefit, it is ethically complex to conduct a placebo-controlled trial, therefore we propose to use a comparator group of patients who have been treated at UVA Medical Center prior to the start of this trial.

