4.2 Exclusion Criteria for Plasma Recipients

- Patients requiring mechanical ventilation or >6 liters per minute nasal cannula oxygen
- Patients on other anti-COVID-19 treatment trials (for example, those being treated with tocilizumab (anti-IL-6 receptor), Siltuximab (anti-IL-2), or Remdesivir).
- A pre-existing condition or use of a medication that, in the opinion of the site investigator, may place the individual at a substantially increased risk due to study participation
- Contraindication to transfusion or history of prior reactions to transfusion blood products.
- Medical conditions for which receipt of 500-600 mL of intravenous fluid may be dangerous to the subject (e.g., decompensated congestive heart failure).

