4.3 Control Group (obtained via chart review and includes control specimens)

Inclusion Criteria:

1. Admitted to a “floor” bed (non-ICU bed) at UVAMC on/after March 30, 2020 due to confirmed COVID-19 disease
2. Age \geq 18 years of age

Exclusion Criteria:

1. Requiring mechanical ventilation or >6 liters per minute nasal cannula upon admission
2. Participation in other interventional anti-COVID-19 treatment trials
3. Medical conditions for which receipt of 200-400mL of intravenous fluid may be dangerous to the subject (e.g. decompensated congestive heart failure)
4. Receipt of convalescent immune plasma for treatment of COVID-19

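### Control exclusions for other-trial participation and convalescent plasma have no index time, so the matched controls can be selected on treatment started after they would have qualified

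*Combined protocol and SAP*

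**What the plan says.** Section 2.3 commits to a control comparison: "Participants will be compared to a historical control group via retrospective chart review". Section 7.1 sets the control group at 29 patients matched on gender and on age within 5 years.

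Section 4.3 defines who may be a control. Of its four exclusions, the first is dated: "Requiring mechanical ventilation or >6 liters per minute nasal cannula upon admission". The second, "Participation in other interventional anti-COVID-19 treatment trials", and the fourth, "Receipt of convalescent immune plasma for treatment of COVID-19", are not. The control list in the section 1.0 summary has an undated plasma criterion, "No receipt of convalescent plasma", and no exclusion for other trials. No section defines an index time for a control.

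For recipients, section 4.2 excludes "Patients on other anti-COVID-19 treatment trials", and section 10.2 requires all eligibility criteria to be met before enrolment. Under section 10.9, a recipient who stops after at least one infusion is a discontinuation and is not replaced.

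**The concern.** Chart review is done when the whole hospital course is known, so an exclusion without a date can be triggered by something that happened after the outcome. Take a floor patient who qualifies on admission, moves to the ICU on day 4, and then enters another COVID-19 trial or is given plasma outside this study. On the natural reading of section 4.3 that patient leaves the control pool, and the ICU transfer goes too. A recipient with the same later course has no stated rule removing him or her.

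Controls would then be chosen partly on treatment given in response to a primary endpoint. What is at stake is the control ICU-transfer rate and the control 28-day mortality, and so the matched comparison of both. The plan itself expects such crossover to be possible: the recipient exclusions in section 1.0 name several trial drugs and allow for trials that start later.

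**Working it through.** **1. Are the exclusions open-ended?** Three features of the text bear on this.
- Exclusion 1 in section 4.3 carries a date and exclusions 2 and 4 do not, so the omission is not the list's general style.
- Selection is retrospective, so later events are visible to the person applying the criteria.
- Plasma for COVID-19 is given in hospital in this plan. If exclusion 4 meant status on admission, it would exclude almost nobody.

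The whole-stay reading is therefore near-certain for plasma. For other trials it is likely, but rests only on the first two features.

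**2. Are recipients treated the same way?** Section 4.2 describes present status and section 10.2 fixes the time at enrolment. Section 5.2.5 prohibits the medications named in the exclusion criteria during study treatment. That governs conduct; neither it nor any other section removes a recipient from analysis for later trial entry.

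**3. The plan's own figure.** Sections 7.1 and 9.1 give 29 evaluable patients, 80% power, 50% versus 25%, two-sided 0.05. A one-sample normal approximation gives

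n = [(1.96 × √(0.5 × 0.5) + 0.842 × √(0.25 × 0.75)) / 0.25]² = 28.9, so 29, with power 80.1%.

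This reproduces. The printed rule (8 or fewer ICU admissions among 29) uses recipients only, against a constant 50%. No control enters it, so control selection cannot change it.

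**4. How far could the control rate move?** The documents give no crossover rates, so everything here is assumed. Take 60 otherwise eligible floor patients, of whom 30 go to the ICU (the plan's 50%). Let f and g be the shares of ICU and non-ICU patients removed for treatment after they qualified. Then

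control ICU rate = 30(1 − f) / [30(1 − f) + 30(1 − g)].

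| f | g | Control ICU rate |
|---|---|---|
| 0.20 | 0 | 24/54 = 44.4% |
| 0.40 | 0 | 18/48 = 37.5% |
| 0 | 0.20 | 30/54 = 55.6% |
| 0.20 | 0.20 | 24/48 = 50.0% |

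**5. What that does to a two-group comparison.** The plan states no test for the matched comparison. As a stand-in, use 29 versus 29 unmatched, a recipient rate of 25%, two-sided 0.05, and

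power = Φ{[d − 1.96√(2p̄(1 − p̄)/29)] / √[(p₁(1 − p₁) + p₂(1 − p₂))/29]},

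where p₁ and p₂ are the two rates, d their difference and p̄ their mean. A control rate of 50% gives 50.3%. At 44.4% power falls to 34.0%. At 55.6% it rises to 66.8%, but part of that rise is bias.

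**The case against.** The strongest reply has four parts.

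*The whole-stay reading is inferred.* A reader might take section 4.3 to say that controls are excluded for ever receiving plasma or joining a trial, even after deterioration. Those words are not printed, and the recipient criteria in section 4.2 are themselves undated, anchored only by section 10.2. This stands as a limit on wording. For other trials the firm statement is that no index time is given and later entry is the likely reading. For plasma the inference is much stronger.

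*Recipients are not judged purely at entry.* Section 5.2.6 removes a recipient who passes 6 L/min or needs ventilation before infusion, section 5.3 lets the investigator withdraw non-compliant subjects, and the term evaluable is not defined. All true. But section 5.2.6 has no counterpart for controls, which adds an asymmetry and strengthens the case for an index time.

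*Crossover may be rare, and the bias may be conservative.* Section 3.2 describes "a comparator group of patients who have been treated at UVA Medical Center prior to the start of this trial", in which case later plasma would be uncommon. Section 4.3, however, admits any control in a "non-ICU bed) at UVAMC on/after March 30, 2020 due to confirmed COVID-19 disease", with no closing date, so the frequency cannot be judged, and trial entry could select even among earlier patients. Removing deteriorating controls does make plasma look worse, but removing stable ones does the opposite. Patients already in another trial when they would qualify are barred from both groups and do not add to this problem.

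*An untransfused comparator is a legitimate choice.* It is, but defining it by what happens after the starting point is what creates the selection.

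**Conclusion.** The point holds for the matched-control comparison of ICU transfer and 28-day mortality. Followed as written, section 4.3 can select controls on events after the time at which they would have qualified, with no corresponding rule for recipients. It is worth correcting before charts are abstracted.

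Two stronger conclusions are tempting and not supported. A reader might infer that the trial's primary test is biased; the only stated decision rule compares 29 recipients with a fixed 50% and does not use the controls. For the same reason, the 25-point difference in sections 7.1 and 9.1 belongs to that test and is not a yardstick for this bias. A reader might also infer that plasma is made to look better, or worse; the documents do not settle the direction.

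The size is unknown. The rates of 44% and 38% rest on assumed removal of 20% or 40% of ICU controls and no others. Mostly non-ICU removal raises the rate, and equal removal produces no shift.

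**What to change.** - In section 4.3, define a control index time comparable to recipient entry. One option is the same time since admission as the matched recipient's infusion, with the control still on the floor and at or below 6 L/min. This also mirrors the pre-infusion removal in section 5.2.6.
- Apply exclusions 2 and 4 only to trial entry or plasma at or before that time.
- Bring the section 1.0 control list into line with section 4.3. It now has an undated plasma criterion and no other-trial exclusion.
- State that this trial's own recipients are not also used as controls.
- Keep controls who enter a trial or receive plasma after the index time, count their ICU transfers and deaths, and state one rule for later crossover that covers both groups.
- As a sensitivity analysis, report results with and without these controls. Simple censoring at the later treatment should not be relied on, because it is informative if crossover follows deterioration.

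The cost is protocol wording and a second pass over two chart criteria, with no new patients or visits. The downside is that some retained controls will have had later experimental treatment, which mainly affects 28-day mortality.

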1.0 SUMMARY

Background: There are currently no proven treatment options for Coronavirus Disease 2019 (COVID-19) caused by Severe Acute Respiratory Syndrome Coronavirus 2 (SARS-CoV-2). Human convalescent immune plasma infusion (CIP) is an option for treatment of COVID-19.

Clinical Experience: Passive antibody therapy for infections has been used since the late 1800s and prior to the development of antimicrobial therapy in the 1940s^{1,2}. There is some evidence that convalescent plasma can provide neutralizing antibodies to SARS-CoV-2³. Convalescent serum was used in the 2013 Ebola epidemic. A small non-randomized study in Sierra Leone revealed a significant increase in survival for patients treated with convalescent whole blood compared to those who received standard treatment⁴.

Primary Objective: Evaluate whether CIP can reduce progression of critical illness among patients hospitalized for COVID-19

Primary Endpoints:

1. Transfer to the intensive care unit (ICU)
2. 28 day mortality

Secondary Objectives:

1. Evaluate the safety of CIP.
2. Evaluate cellular and humoral responses before CIP treatment and at CIP treatment.
3. Evaluate the effect of CIP as compared to non-transfused immunologic control patients.

Secondary Endpoints:

- Cumulative incidence of serious adverse events during the study period: transfusion reaction (fever, rash), transfusion related acute lung injury (TRALI), transfusion associated circulatory overload (TACO), transfusion related infection
- Rates and duration of SARS-CoV-2 PCR positivity at days 0, 4, 7, 14 and 21.
- Serum or plasma antibody titer¹ to SARS-CoV-2: Day 0, 7, 14, and 28
- Cellular and humoral immune responses at days 0, 7, 14, and 28 days
- Supplemental oxygen free days
- Ventilator free days
- ICU free days
- Sequential organ failure assessment (SOFA) score at days 0, 1, 2, 17, 14, 21, 28
- Need for vasopressors
- Need for renal replacement therapy
- Need for extracorporeal membrane oxygenation (ECMO)
- Hospital length of stay (LOS)
- ICU LOS
- Grade 3 or 4 adverse events (AEs)

Study Design: This is a single arm phase II trial to assess efficacy and confirm safety of infusions of anti-SARS-CoV-2 convalescent plasma in hospitalized patients with acute respiratory symptoms, with or without confirmed interstitial COVID-19 pneumonia by chest Xray or CT. A total of 29 eligible subjects will be enrolled to receive anti-SARS-CoV-2 plasma. Outcomes will be compared to hospitalized controls

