¹ Measured by an anti-SARS-CoV-2 ELISA and serum antibody titer to SARS-CoV-2.

with confirmed COVID-19 disease through retrospective chart review.

In addition, the following Immunologic Controls will be used to meet secondary objectives described above:

1. PBMCs with 5-10 million cryopreserved cells per specimen will be obtained from the prospective COVID 19 Biorepository (2 timepoints per patient t (60 specimens total) and assessed for cellular and humoral immune responses.
2. Serum or plasma 500 UI each from up to 50 patients in the Covid-19 Biorepository will be collected (2 timepoints from each patient) (100 total specimens) will be evaluated for antibody and cytokine responses.

Study Population:

Inclusion Criteria for Enrollment

1. Patients must be 18 years of age or older
2. Patients hospitalized with COVID-19 respiratory symptoms within 72 hours of admission to a "floor" bed (non-ICU bed) and confirmation via SARS-CoV-2 RT-PCR testing.
3. Patient and/or surrogate is willing and able to provide written informed consent and comply with all protocol requirements.
4. Patients with hematologic malignancies or solid tumors are eligible.
5. Patients with autoimmune disorders are eligible.
6. Patients with immunodeficiency and organ or stem cell transplant recipients are eligible.
7. Patients who have received or are receiving hydroxychloroquine or chloroquine are eligible (but will be taken off the drug)
8. Prior use of IVIG is allowed but the investigator should consider the potential for a hyper-coagulable state.

Exclusion Criteria

1. Patients requiring mechanical ventilation or >6 liters per minute nasal cannula oxygen
2. Patients on other anti-COVID-19 trials being treated with tocilizumab (anti-IL-6 receptor), Siltuximab (anti-IL-2), Remdesivir, or other pharmacological trials that may be initiated hereafter.
3. A pre-existing condition or use of a medication that, in the opinion of the site investigator, may place the individual at a substantially increased risk due to study participation
4. Contraindication to transfusion or history of prior reactions to transfusion blood products.
5. Medical conditions for which receipt of 500-600 mL of intravenous fluid may be dangerous to the subject (e.g., decompensated congestive heart failure).

Clinical Controls (obtained via chart review):

1. Admitted to a "floor" bed (non-ICU bed) at UVAMC on/after March 30, 2020 due to confirmed COVID-19 disease using SARS-CoV-2 RT-PCR Testing

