7.0 STATISTICAL CONSIDERATIONS

7.1 Statistical Analyses

Twenty-nine evaluable patients will have 80% power to declare a significant decrease in ICU admissions from a historical control of 50% of hospitalized patients to 25% with a two-sided type I error of 0.05 (reject ICU admission rate=50% if only 8 or less patients are admitted to ICU among 29 evaluable patients). The historic control group will consist of 29 patients who are gender and age (within 5 years) matched.

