7.3 Endpoints

7.3.1 Primary Endpoints

- Transfer to ICU
- 28 day mortality

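### Chart-review controls are excluded for fluid intolerance at 200-400 mL but plasma recipients at 500-600 mL: a minor, easily removed comparability defect

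*Combined protocol and SAP*

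**What the plan says.** Recipients are excluded under Section 4.2 for "Medical conditions for which receipt of 500-600 mL of intravenous fluid may be dangerous to the subject"; the Summary's recipient exclusions give the same volume. Section 4.3, exclusion 3, applies to chart-review controls and reads "Medical conditions for which receipt of 200-400mL of intravenous fluid may be dangerous to the subject". Both criteria offer decompensated congestive heart failure as the example.

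The Summary also has a short list of clinical controls. It covers floor admission with PCR-confirmed disease, adult age, and, as its last item, "No receipt of convalescent plasma". It gives no fluid criterion.

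On dose, the Summary's drug paragraph and Section 5.1 plan one or two units of about 200 mL each, so about 200-400 mL in total.

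On use of the controls, the Summary states "Outcomes will be compared to hospitalized controls" and Section 2.3 states "Participants will be compared to a historical control group via retrospective chart review". Section 7.1 adds: "The historic control group will consist of 29 patients who are gender and age (within 5 years) matched". Section 7.3.1 lists transfer to the ICU and "28 day mortality" as the primary endpoints.

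**The concern.** Two groups that are to be compared should pass the same eligibility screen wherever a chart allows it. Here they do not. Any condition that makes 200-400 mL dangerous would also make 500-600 mL dangerous, but the converse does not hold. The asymmetry therefore runs one way: on this rule, patients with intermediate fluid tolerance can enter only as controls. Such patients may be frailer, which is an inference and not something the documents state. If so, they would raise the control rates of ICU transfer and death slightly and make plasma look slightly better. Matching on gender and age does not remove the difference.

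The stake is greatest for 28-day mortality. The plan states no fixed benchmark for it, so the chart-review controls are its only stated comparator. Section 3.2 also offers this comparator group in place of a placebo arm, so comparable eligibility is one of the few protections the design has.

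**Working it through.** **1. The criteria side by side**

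| Source | Group | Excluded if this volume may be dangerous |
|---|---|---|
| Summary; Section 4.2 | Recipients | 500-600 mL |
| Section 4.3, exclusion 3 | Chart-review controls | 200-400 mL |
| Summary; Section 5.1 | (planned dose) | about 200-400 mL |

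A patient who tolerates 400 mL but not 500-600 mL is eligible as a control and ineligible as a recipient. No patient is in the opposite position on this rule. The recipients' limit exceeds the maximum dose by 500 - 400 = 100 mL to 600 - 400 = 200 mL. No section explains the difference or reconciles the two limits.

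**2. Does it touch the sized test?**

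Inputs from Sections 7.1 and 9.1: null ICU rate 0.50, alternative 0.25, two-sided alpha 0.05, power 80%. With a one-sample normal approximation:

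n = [(1.96 x sqrt(0.25) + 0.842 x sqrt(0.1875)) / 0.25]^2 = 28.9, rounded up to 29; power at 29 is 80.1%.

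The plan's figure reproduces on that approximation. (The exact binomial power of the 8-of-29 rule is 71.3%; that is a separate matter.) The exact chance of 8 or fewer ICU admissions among 29 at a true rate of 0.50 is 0.012. None of these formulas contains a control rate, so changing the control criterion changes none of them.

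**3. How far could the control rates move?**

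The documents give neither the number of patients between the limits nor their risks. The following inputs are assumptions: 0 to 3 of 29 controls lie between the limits, their ICU risk is 0 to 30 points higher, and their 28-day mortality is 0 to 20 points higher.

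Shift in control rate = (n / 29) x risk difference; extra events = n x risk difference.

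| Outcome | n | Risk difference | Shift | Extra events |
|---|---|---|---|---|
| ICU | 0 | any | 0 | 0 |
| ICU | 1 | 0.10 | 0.0034 | 0.1 |
| ICU | 2 | 0.20 | 0.0138 | 0.4 |
| ICU | 3 | 0.30 | 0.0310 | 0.9 |
| Death | 0 | any | 0 | 0 |
| Death | 3 | 0.20 | 0.0207 | 0.6 |

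**4. Scale**

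Standard error of a proportion in 29 controls:

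- ICU at 50%: sqrt(0.5 x 0.5 / 29) = 0.0928
- Mortality at an assumed 10%: sqrt(0.1 x 0.9 / 29) = 0.0557
- Mortality at an assumed 20%: sqrt(0.2 x 0.8 / 29) = 0.0743

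The largest shifts are about a third of these: 3.1 / 9.3 = 0.33 for ICU, and 2.1 / 7.4 = 0.28 to 2.1 / 5.6 = 0.37 for mortality.

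**The case against.** The best defence is that the gap may be almost empty. Both criteria are clinical judgements with the same heart-failure example, and a chart reviewer is unlikely to separate intolerance at 400 mL from intolerance at 500 mL reliably. This stands, and it is why the point is minor. It does not explain why two compared groups should have different written limits.

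A second defence is that 200-400 mL is simply the dose. That may well be how the control wording arose, and it bears on which limit to keep. A reader might go further and infer that the recipients' 500-600 mL is a leftover error. The documents do not say so; a deliberate margin above the dose is equally possible.

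A third is that no stated decision depends on the comparison. Section 9.1 tests ICU admission against a fixed 50%, plans frequencies and percentages for categorical clinical endpoints, and names no recipient-versus-control test of mortality. This also stands. The comparison is nevertheless announced, and its reading depends on who the controls are.

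A reader might also take the Summary's control list as a rival definition that admits any fluid-intolerant patient. The text does not support that. The list also leaves out the oxygen or ventilation exclusion and the other-trials exclusion in Section 4.3, so it reads as an abridgement. Section 10.2, although written for enrolled subjects, points to Section 4.0 for the full eligibility requirements.

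**Conclusion.** The inconsistency is real and its direction on this one rule is clear. It is a minor comparability defect. On the stated assumptions it adds 0 to 0.9 ICU event (0 to 3.1 percentage points) and 0 to 0.6 death (0 to 2.1 points) among 29 controls. Zero is a credible value in both cases.

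A reader might infer that the trial as a whole is biased in favour of plasma. The documents do not establish a net direction. Other rules apply to recipients only: respiratory symptoms, the 72-hour window and consent (Section 4.1); investigator-judged risk and transfusion contraindication (Section 4.2); and removal before infusion if oxygen need rises or ventilation is required (Section 5.2.6). Some may act the other way; for example, controls without respiratory symptoms may be milder cases.

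**What to change.** Use one identical fluid criterion for both groups. By default, replace exclusion 3 of Section 4.3 with the recipients' wording, "Medical conditions for which receipt of 500-600 mL of intravenous fluid may be dangerous to the subject", keep the same heart-failure example, and add that it is judged from the chart as of admission. Editing the control text leaves any safety margin in the recipients' exclusion untouched. That matters because circulatory overload is a named transfusion risk in Section 5.6.3 and a stopping event in Section 15.0. If the sponsor instead changes the recipients' limit, for example to match the dose, the control criterion should follow it.

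Have the Summary's clinical-control list refer to Section 4.3 in full. Adding only a fluid line would leave it without the oxygen or ventilation and other-trials exclusions.

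The cost is one changed line, one cross-reference and one check at chart selection. A few charts may drop out and need replacements matched on age and gender, and fluid tolerance can only be judged roughly from a chart. The change removes one avoidable difference; it does not make the groups equivalent.
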